8.2 SAFETY ASSESSMENTS

Assessment of Adverse and Serious Adverse Events:

AEs and SAEs will be monitored by acupuncturists during acupuncture treatment sessions, and by study staff during the 4-week and 12-week post-treatment visits. The acupuncturists and research staff will immediately notify the Principal Investigator and utilize the eCRF to record any AEs or SAEs. The PI and the study physician will review and categorize all AEs or SAEs and report them accordingly, as discussed below.

8.3 ADVERSE EVENTS AND SERIOUS ADVERSE EVENTS

8.3.1 DEFINITION OF ADVERSE EVENTS

This protocol uses the definition of AE from 21 CFR 312.32 (a): any untoward medical occurrence associated with the use of an intervention in humans, whether or not considered intervention-related.

8.3.2 DEFINITION OF SERIOUS ADVERSE EVENTS

This protocol uses the definition of SAE from 21 CFR 312.32 (a): An AE or suspected adverse reaction is considered "serious" if, in the view of either the investigator or study clinician, it results in any of the following outcomes: Death, a life-threatening AE, inpatient hospitalization or prolongation of existing hospitalization, a persistent or significant incapacity or substantial disruption of the ability to conduct normal life functions, or a congenital anomaly/birth defect. Important medical events that may not result in death, be life-threatening, or require hospitalization may be considered serious when, based upon appropriate medical judgment, they may jeopardize the patient or subject and may require medical or surgical intervention to prevent one of the outcomes listed in this definition.

8.3.3 CLASSIFICATION OF AN ADVERSE EVENT

8.3.3.1 SEVERITY OF EVENT

For AEs not included in the protocol defined grading system, the following guidelines will be used to describe severity.

- 1. **Mild** Events require minimal or no treatment and do not interfere with the participant's daily activities.
- 2. **Moderate** Events result in a low level of inconvenience or concern with the therapeutic measures. Moderate events may cause some interference with functioning.
- 3. **Severe** Events interrupt a participant's usual daily activity and may require systemic drug therapy or other treatment. Severe events are usually potentially life-threatening or incapacitating. Of note, the term "severe" does not necessarily equate to "serious".

8.3.3.2 RELATIONSHIP TO STUDY INTERVENTION/EXPERIMENTAL MANIPULATION

All AEs will have their relationship to study procedures, including the intervention, assessed by an appropriately-trained clinician based on temporal relationship and his/her clinical judgment. The degree of certainty about causality will be graded using the categories below.

Definitely Related – There is clear evidence to suggest a causal relationship, and other possible
contributing factors can be ruled out. The clinical event, including an abnormal laboratory test
result, occurs in a plausible time relationship to study procedures administration and cannot be
explained by concurrent disease or other drugs or chemicals. The response to withdrawal of the
study procedures should be clinically plausible. The event must be pharmacologically or
phenomenologically definitive.

- Probably Related There is evidence to suggest a causal relationship, and the influence of other
 factors is unlikely. The clinical event, including an abnormal laboratory test result, occurs within a
 reasonable time after administration of the study procedures, is unlikely to be attributed to
 concurrent disease or other drugs or chemicals, and follows a clinically reasonable response on
 withdrawal.
- Potentially Related There is some evidence to suggest a causal relationship (e.g., the event occurred within a reasonable time after administration of study procedures). However, other factors may have contributed to the event (e.g., the participant's clinical condition, other concomitant events). Although an AE may rate only as "possibly related" soon after discovery, it can be flagged as requiring more information and later be upgraded to "probably related" or "definitely related", as appropriate.
- Unlikely to be related A clinical event, including an abnormal laboratory test result, whose temporal relationship to study procedures administration makes a causal relationship improbable (e.g., the event did not occur within a reasonable time after administration of the study procedures) and in which other drugs or chemicals or underlying disease provides plausible explanations (e.g., the participant's clinical condition, other concomitant treatments).
- Not Related The AE is completely independent of study procedures administration, and/or
 evidence exists that the event is definitely related to another etiology. There must be an
 alternative, definitive etiology documented by the clinician.

8.3.3.3 EXPECTEDNESS

A clinician with expertise in TBI, CPTH, and acupuncture will be responsible for determining whether an AE is expected or unexpected. An AE will be considered unexpected if the nature, severity, or frequency of the event is not consistent with the risk information previously described for the study procedures.

8.3.4 TIME PERIOD AND FREQUENCY FOR EVENT ASSESSMENT AND FOLLOW-UP

The occurrence of an AE or SAE may come to the attention of study personnel during study visits and interviews of a study participant.

All AEs, not otherwise precluded per the protocol, will be captured on the appropriate eCRF. Information to be collected includes event description, time of onset, clinician's assessment of severity, relationship to study procedures (assessed only by those with the training and authority to make a diagnosis), and time of resolution/stabilization of the event. All AEs occurring while on study will be documented appropriately regardless of relationship. All AEs will be followed to adequate resolution.

Any medical or psychiatric condition that is present at the time that the participant is screened will be considered as baseline and not reported as an AE. However, if the study participant's condition deteriorates at any time during the study, it will be recorded as an AE.

Changes in the severity of an AE will be documented to allow an assessment of the duration of the event at each level of severity to be performed. Documentation of onset and duration of each episode will be maintained for AEs characterized as intermittent.

Study staff will record events with start dates occurring any time after the first acupuncture treatment session until the 12-week post-treatment visit. At each acupuncture treatment visit (after the 1st) and the 4-week and 12-week post-treatment visits, study staff will inquire about the occurrence of AE/SAEs since the last visit. All reported events will be monitored until the 12-week post-treatment visit. Any reported event that is definitely or probably related to the intervention will be followed until resolution or stabilization.

8.3.5 ADVERSE EVENT REPORTING

In consultation with the Principal Investigator (PI) and the study clinician, a trained member of the study team will be responsible for conducting an evaluation of an AE and shall report the results of such evaluation to the reviewing IRB either at the time of continuing review or within 10 working days of becoming aware of the event if the event is considered to be serious or meets the definition of an unanticipated problem involving risks to study subjects or others.

8.3.6 SERIOUS ADVERSE EVENT REPORTING

In consultation with the PI and the study clinician, a trained member of the study team will be responsible for conducting an evaluation of a SAE and shall report the results of such evaluation to the reviewing IRB as soon as possible, but in no event later than 10 working days after the investigator first learns of the event.

8.3.7 REPORTING EVENTS TO PARTICIPANTS

Following IRB review of any AEs or SAEs, the PI will follow the IRB's recommended actions. This may include, but is not limited to, modifying the informed consent document or process, re-consenting current participants, providing information to past or current participants (e.g. whenever the information may relate to the participant's willingness to continue participants), and modifications to the protocol/research plan.

8.3.8 EVENTS OF SPECIAL INTEREST

N/A

8.3.9 REPORTING OF PREGNANCY

Women who are currently pregnant, lactating, or planning to become pregnant during the study are excluded from this study. This is due to the hormonal changes that may alter headache patterns. If any participant who is still undergoing acupuncture treatment expectedly or unexpectedly becomes pregnant while active in the trial, the participant will be withdrawn from the study by the Principal Investigator. The participant will be asked to complete an early withdrawal phone call in 7-14 days from the date the intervention was discontinued for safety follow-up.

If any participant who has completed all acupuncture treatment sessions expectedly or unexpectedly becomes pregnant, the participant may remain in the study until study completion.

8.4 UNANTICIPATED PROBLEMS

8.4.1 DEFINITION OF UNANTICIPATED PROBLEMS

This protocol uses the definition of Unanticipated Problems as defined by the Office for Human Research Protections (OHRP). OHRP considers unanticipated problems involving risks to participants or others to include, in general, any incident, experience, or outcome that meets **all** of the following criteria:

- Unexpected in terms of nature, severity, or frequency given (a) the research procedures that are
 described in the protocol-related documents, such as the IRB-approved research protocol and
 informed consent document; and (b) the characteristics of the participant population being
 studied;
- 2. Related or possibly related to participation in the research ("possibly related" means there is a reasonable possibility that the incident, experience, or outcome may have been caused by the procedures involved in the research); and
- 3. Suggests that the research places participants or others at a greater risk of harm (including physical, psychological, economic, or social harm) than was previously known or recognized.

8.4.2 UNANTICIPATED PROBLEMS REPORTING

The PI will report unanticipated problems (UPs) to the reviewing IRB. The UP report will include the following information:

- Protocol identifying information: protocol title and number, PI's name, and the IRB project number
- A detailed description of the event, incident, experience, or outcome
- An explanation of the basis for determining that the event, incident, experience, or outcome represents an UP
- A description of any changes to the protocol or other corrective actions that have been taken or are proposed in response to the UP

To satisfy the requirement for prompt reporting, UPs will be reported using the following timeline:

• UPs will be reported to the IRB as soon as possible, but no later than 10 working days after the investigator first learns of the event

8.4.3 REPORTING UNANTICIPATED PROBLEMS TO PARTICIPANTS

Following IRB review of any unanticipated problems, the PI will follow the IRB's recommended actions. This may include, but is not limited to, modifying the informed consent document or process, reconsenting current participants, providing information to past or current participants (e.g. whenever the information may relate to the participant's willingness to continue participants), and modifications to the protocol/research plan.

9 STATISTICAL CONSIDERATIONS

9.1 STATISTICAL HYPOTHESES

Primary Endpoint: Number of headache days over 4 weeks

We hypothesize that 10 treatments will greater alleviate headaches when compared to 5 treatments over a 5-week treatment period. We also hypothesize that both treatment groups will have decreased headaches. Alternatively, our null hypothesis is that there will be no difference between 5 and 10 treatments.

 Secondary Endpoints: 1) Adverse or Serious Adverse Events and 2) Completion of treatment durations and sessions

We hypothesize that acupuncture will be safe and tolerated in both groups.

• Exploratory Endpoints: 1) Sleep, 2) Quality of life, 3) Headache Outcomes, and 4) Medications

9.2 SAMPLE SIZE DETERMINATION

We require 18 subjects in each study group to achieve 80% power at a 5% significance level for our primary hypothesis (PASS software version 11). The primary analysis is a a two-sided two-sample t-test comparing the mean number of headache days over 4 weeks from a parallel-group design. We hypothesize that, while both groups will have decreased headaches, 10 treatments will greater alleviate headaches when compared to 5 treatments over a 5-week treatment period. For analysis purposes, we will analyze the data such that the opposite could be shown (5 treatments better reduces headaches). The null hypothesis is that there will be no difference between treatment groups. To conduct the power calculation, we assumed an equal standard deviation of 4.47, 33 equivalence limits of ± 1 SD, and a true difference between means of 0. No interim analyses are planned. The potential effect on our power if our estimates for the effect size are inaccurate are displayed in the table below.

N	δ	Σ	Power	Alpha
36	4	4.5	0.742	0.05
36	4.5	4.5	0.835	0.05
36	5	4.5	0.903	0.05

N = total sample size; δ = treatment effect (change); σ = standard deviation.

Based on preliminary estimates, we do not anticipate difficulty recruiting 40 subjects. HealthPartners Physical Medicine and Rehabilitation physicians see approximately 25 individuals with CPTH per month at the Neuroscience Center. Therefore we will need a 16% enrollment rate to reach our recruitment goal in the allotted time frame. In addition, we also plan to recruit and enroll from other HealthPartners clinics and within the community. If we see a 20% reduction in sample size due to dropout, withdrawal, or missing data, our power will be 75.8% to detect a similar effect size. This, and other possible changes in power due to attrition, are listed in the table below.

N	μ1	μ2	δ	σ	Power	Alpha
28	26	21.5	4.5	4.5	0.727	0.05

30	26	21.5	4.5	4.5	0.758	0.05
32	26	21.5	4.5	4.5	0.787	0.05
36	26	21.5	4.5	4.5	0.835	0.05

N = total sample size; μ 1 = mean of 5 treatment group; μ 2 = mean of 10 treatment group; δ = treatment effect (change); σ = standard deviation.

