2 INTRODUCTION

2.1 BACKGROUND & STUDY RATIONALE

Chronic post-traumatic headache (CPTH) after a mild traumatic brain injury (mTBI) is extremely debilitating, dramatically impacts function and quality of life, and is the most frequent type of chronic pain reported after injury.¹ It has been estimated that approximately 17.1 million Americans suffer a traumatic brain injury (TBI) each year,² with CPTH estimated to occur in 57.8% of these individuals.³ CPTH presents as: 1) tension-like (mild-moderate dull pain), 2) migraine headache (moderate-severe throbbing pain), or 3) combined tension-like and migraine headache.¹ On average, the number of reported headache days each month for individuals suffering from CPTH is 26,⁴ which is almost daily. Individuals suffering from CPTH are more likely to have post-traumatic stress disorder, cognitive symptoms, and somatic symptoms.⁴ They are also more likely to perceive difficulties in their physical and social function.⁴ Consequently, it is not surprising that CPTH is extremely agonizing and frustrating for individuals with mTBI.

There are currently no FDA approved pharmacological treatments specifically for CPTH and the long-term effects of pharmacologic treatments on recovery after TBI are unclear. Thus, individuals are typically prescribed medications that target the particular type of headache (e.g. triptan for a migraine headache). Non-narcotic analgesics, nonsteroidal anti-inflammatory drugs (NSAIDs), and triptans are often prescribed for headache and migraine treatment and have been recommended to be coupled with non-pharmacological treatments, such as physical therapy, biofeedback, and relaxation training. However, because the long-term effects of pharmacologic treatments on recovery after TBI are unclear, non-pharmacologic or behavioral treatments for CPTH are very appealing.

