4 STUDY DESIGN

4.1 OVERALL DESIGN

Study Design:

This study is an unblinded, uncontrolled randomized, 2-arm clinical trial.

Hypotheses:

Primary Hypothesis: We hypothesize that both treatment groups will have decreased headaches. **Secondary Hypothesis:** We hypothesize that acupuncture will be safe and tolerated in both groups.

Randomization:

Prior to the first acupuncture treatment visit, participants will be randomized into two treatment groups. Randomization is explained in **Section 6.3**.

Acupuncture Treatment Groups:

Group 1: 18 participants will receive acupuncture treatment 1x per week for 5 weeks = 5 total. **Group 2:** 18 participants will receive acupuncture treatment 2x per week for 5 weeks = 10 total.

Study Intervention:

Acupuncture treatment will consist of a standardized treatment protocol designed for this study. Specifically, 18 needles will be inserted into specific areas of the body for a duration of 30 minutes. Additional details of the treatment are discussed in **Section 6.1**.

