5.5 STRATEGIES FOR RECRUITMENT AND RETENTION

Recruitment: Individuals with mTBI suffering from CPTH will be recruited by physician and therapist referrals from HealthPartners' clinics. We will also advertise our research study by distributing flyers to HealthPartners' physicians and throughout HealthPartners' clinics. Recruitment flyers will also be provided to our community partners for example, the Minnesota Brain Injury Alliance, TRIA, and Allina Health. If we encounter difficulties with recruitment, we plan to submit an amendment to the IRB to contact HealthPartners patients and members and invite them to participate.

To reach our target enrollment, we anticipate that we will need to screen 100 people, of those 50 individuals will sign the informed consent, and of those 40 individuals will be randomized to treatment groups. We expect that we will enroll approximately 35% (~13) women and 65% (~23) men, primarily between the ages of 41-84, and approximately 80% will be white. Values are based on our Regions Hospital Rehabilitation census data.

Remuneration: Participants will be provided gift cards totaling \$50 per person for completing certain time points of the research study. Specifically, after completing all acupuncture treatment visits, participants will receive a \$25 gift card. After completion of the 12-week post-treatment visit (end of study visit) participants will receive another \$25 gift card.

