9.4.2 ANALYSIS OF THE PRIMARY ENDPOINT(S)

The number of headache days per 4 weeks will be captured via a headache diary. The primary outcome, change in number of headache days per 4 weeks between the pre-treatment assessment and 4-week post treatment assessment, will be compared using a two sample t-test. We will present the mean change by group with corresponding standard deviations. If baseline differences are found between study groups, they will be adjusted for using a linear regression model. In addition, a mixed-model analysis of variance (ANOVA) will be performed with data from all three time points. The outcome will be number of headache days per 4 weeks and it will be adjusted for group, time, and a group*time interaction. If significant interactions exist, line plots and post hoc tests will be used to define the nature of the interaction.

Prior to analysis, we will plot our outcomes to examine their distribution and decide whether we should consider non-parametric analyses. Only subjects with complete data from both pre-treatment assessment and 4-week post treatment assessment will be included in the final analysis. Data will be analyzed per an intent-to-treat approach regardless of actual treatment received. If a large proportion of missing data is noted, we will compare baseline characteristics of subjects who completed the treatment with those who were lost to follow-up.

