10.4 PROTOCOL AMENDMENT HISTORY

Version	Date	Description of Change	Brief Rationale
2.0	12/12/2019	Response to initial IRB Review	Response to initial IRB Review
3.0	09/17/2020	Addition of 3 healthy volunteer protocol practice participants, inperson visits changed to phone visits (except acupuncture treatment visits), consent and assessments to be completed electronically, COVID-19 changes (including PPE) will align with NSC clinic policies and procedures.	COVID-19 Pandemic
4.0	02/16/2021	Changes to the inclusion/exclusion critieria. (Changed to: No acupuncture while enrolled in the study and mTBI diagnosis within 2 years.)	COVID-19 Pandemic; slow recruitment/enrollment
5.0	03/30/2021	Change to inclusion criteria. Change upper limit from 65 to 70.	COVID-19 Pandemic; slow recruitment/enrollment
6.0	05/04/2021	Change to acupuncture treatment protocol- allow for removal of needles or e-stim due to extreme pain/discomfort. Also update AE reporting.	Recent minor protocol deviation due to removal of estim due to pain/discomfort.
7.0	07/29/2021	Addition of 2 healthy volunteer patients to train Twin City Acupuncture (TCA) acupuncturists on the study protocol.	We are adding a consulting agreement for the study to allow 2 TCA acupuncturists to assist with the study treatments.
8.0	09/07/2021	Remove inclusion criteria: "Stable medication regimen for ≥1 months and agree to adhere to his or her current medication treatment regimen through study participation."	Throughout enrollment, we learned that participants require more flexibility with prescription medication changes. We plan to continue to record and monitor medications for all patients.
9.0	05/26/22	Update PN Address	Address was incorrect
10.0	02/16/23	Remove PN location and add Como Clinic and Healing Response Acupuncture	Change in locations for acupuncture treatment
11.0	03/03/23	Add 2 healthy volunteers, increase enrollment to 40 (due to withdrawals), Add [name] & [name].	Add 2 healthy volunteers, increase enrollment to 40 (due to withdrawals), Add [name] & [name].

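### Section 9.2 derives 18 per arm and 80% power from equivalence-test inputs although a two-sided difference test is planned, and its 75.8% power does not correspond to a 20% loss from 36 or 40

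*Combined protocol and SAP*

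**What the plan says.** Section 9.2 asks for 18 participants per arm to reach 80% power at the 5% level. It names the primary analysis as a "two-sided two-sample t-test comparing the mean number of headache days over 4 weeks", with a null hypothesis of no difference between arms. The inputs it gives for the calculation are an SD of 4.47 in both arms, "equivalence limits of ± 1 SD, and a true difference between means of 0".

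Two tables follow. The first gives power at N=36 for differences of 4, 4.5 and 5 days: 0.742, 0.835 and 0.903. The second holds the difference at 4.5 days (group means 26 and 21.5) and gives 0.727, 0.758, 0.787 and 0.835 for N = 28, 30, 32 and 36. On attrition the text reads "If we see a 20% reduction in sample size due to dropout, withdrawal, or missing data, our power will be 75.8" (per cent).

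The number randomised differs between sections. The schema in 1.2 randomises 36, and 4.1 states "18 participants will receive acupuncture treatment 1x per week for 5 weeks", with 18 in the other arm as well. Section 1.1 gives 40, and 5.5 states "of those 40 individuals will be randomized to treatment groups".

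Section 9.4.2 defines the variable to be tested as the "change in number of headache days per 4 weeks between the pre-treatment assessment and 4-week post treatment assessment", and restricts the analysis to participants with both assessments.

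**The concern.** There are three separate problems.

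1. **Basis of the 80%.** Equivalence limits and a true difference of 0 belong to an equivalence test, in which power is the chance of showing that the arms are alike. The plan contains no equivalence hypothesis or test. The sentence that justifies the sample size therefore names no difference to be detected.
2. **Attrition.** The power quoted for a 20% loss is the table's N=30 row, and 30 is not 20% below either of the plan's totals. Because 9.4.2 analyses only complete cases, the evaluable number determines the power, so this figure matters.
3. **Which SD.** The test is on change scores, but the second table in 9.2 enters group means of 26 and 21.5. The value 26 matches the monthly count in section 2.1, where "the number of reported headache days each month for individuals suffering from CPTH is 26". The calculation therefore reads as one on single 4-week counts. If so, the power of the change-score test depends on a pre/post correlation that the plan does not give.

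At stake is whether the stated power figures describe the trial that will be analysed, and whether the adequacy of N can be confirmed from the text.

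**Working it through.** **Inputs.** From 9.2: SD 4.47, limits ±1 SD = ±4.47 days, true difference 0, alpha 0.05, and tabulated differences of 4, 4.5 and 5 days. From 6.3: 1:1 allocation.

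**Step 1: reproduce 18 per arm and 80%.** With two one-sided tests at 5% each, equivalence is declared when |d| + t(0.95; 2n−2) · s · √(2/n) < 4.47, where d is the observed difference and s the pooled SD. At a true difference of 0, power is the average over the distribution of s of 2Φ[(4.47 − t · s · √(2/n)) / (4.47 · √(2/n))] − 1, counting only values of s for which the numerator is positive.

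| n per arm | Equivalence power |
|---|---|
| 17 | 0.773 |
| 18 | 0.805 |
| 19 | 0.832 |

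Eighteen is the smallest n that reaches 80%, so the stated figure is the equivalence figure. The planned t-test at a true difference of 0 rejects with probability 0.05.

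**Step 2: reproduce the tables.** For the two-sided t-test the noncentrality is δ / (σ · √(2/n)). With δ = 4.5, σ = 4.47 and n = 18, this is 4.5 / (4.47 × 0.3333) = 4.5 / 1.49 = 3.02. On 34 degrees of freedom the critical value is 2.032, and power is 0.835.

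| N | δ | Printed | Recomputed (σ = 4.47) |
|---|---|---|---|
| 36 | 4 | 0.742 | 0.7415 |
| 36 | 4.5 | 0.835 | 0.8349 |
| 36 | 5 | 0.903 | 0.9031 |
| 28 | 4.5 | 0.727 | 0.7271 |
| 30 | 4.5 | 0.758 | 0.7585 |
| 32 | 4.5 | 0.787 | 0.7868 |

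The tables come from the planned test, and their printed σ of 4.5 is 4.47 rounded (σ = 4.5 would give 0.830 at N=36). At a difference of exactly 1 SD, power is 0.807 with 17 per arm and 0.830 with 18.

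**Step 3: attrition.** N=30 is a loss of 1 − 30/36 = 16.7% from 36, or 1 − 30/40 = 25% from 40. A 20% loss is:

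- from 36: 0.8 × 36 = 28.8, giving 72.7% at 28 and 74.3% at 29 (15 and 14 per arm);
- from 40: 0.8 × 40 = 32, giving 78.7%.

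The stated 75.8% is 1.5 to 3.1 points too high on the first base and 2.9 points too low on the second. It may have arisen as 36/1.2 = 30, but that is not a 20% reduction. Section 5.5 also mixes the bases: it randomises 40 but projects about 13 women and 23 men, which sum to 36.

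**Step 4: if 4.47 is the SD of a single count.** Assume the same SD at both times and correlation r. The SD of the change is then 4.47 · √(2(1 − r)). The values of r are assumptions; the plan gives none.

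| r | SD of change | Power, N=36 | Power, N=32 |
|---|---|---|---|
| 0.3 | 5.29 | 69.8% | 64.4% |
| 0.5 | 4.47 | 83.5% | 78.7% |
| 0.7 | 3.46 | 96.6% | 94.5% |

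For 80% power at 4.5 days, the SD of change can be at most 4.68 with 36 evaluable (r at least 0.45) or 4.40 with 32 evaluable (r at least 0.52).

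**The case against.** The strongest reply is that nothing in the conduct of the trial turns on the first two points. The tables sit directly under the faulty sentences and already give the right test and powers. Eighteen per arm exceeds 80% for the planned test at a 1 SD difference. The attrition error is about three points at most, and it is conservative if the base is 40. All of this stands, and it limits the weight of the finding. It does not make the two sentences correct.

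On the SD, the value carries a citation that cannot be checked here, and both table legends label the effect as a change. That label is ambiguous, because the tabulated means are 26 and 21.5, which are counts. The third point is therefore a conditional one and not a demonstrated loss of power.

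On 36 versus 40, the amendment history in 10.4 says enrolment was raised because of withdrawals, which fits 36 as the required number and 40 as the target. That explains the difference, but 1.2 and 4.1 still carry the lower figure as the number randomised or treated.

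Finally, replacing the rationale after enrolment has begun could look like rewriting it after the fact. A dated amendment that records what was changed and why answers that.

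**Conclusion.** The concern holds and should be fixed. The 80% at 18 per arm is the power of an equivalence test (80.5%) that the trial will not perform. The planned t-test has 83.5% power at 18 per arm if the difference is 4.5 days and the SD of the tested variable is 4.47. On those assumptions the trial is not undersized: the stated basis is wrong, not the N.

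The 75.8% does not match a 20% loss from either total. The correct values are 72.7% to 74.3% from 36 and 78.7% from 40, at the same difference and SD.

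Whether power reaches 80% for the change score cannot be confirmed from the plan. If 4.47 is the SD of one 4-week count, equal at both times, power falls below 80% when the pre/post correlation is below about 0.45 with 36 evaluable, or about 0.52 with 32.

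**What to change.** By dated amendment to 9.2:

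- Remove the equivalence limits and the true difference of 0. State the two-sided two-sample t-test, alpha 0.05, a difference of 4.5 days with its justification, SD 4.47, 18 evaluable per arm and 83.5% power.
- Say whether 4.47 is the SD of the change from pre-treatment to 4 weeks post-treatment. If it is the SD of a single count, give power over a range of correlations, as in the last table of the working.
- Settle the randomised number across 1.1, 1.2, 4.1 and 5.5, and distinguish it from the number needed for analysis.
- Correct the attrition sentence to match: 32 of 40 gives 78.7%, or 28 to 29 of 36 gives 72.7% to 74.3%.

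In the same amendment, align the primary hypothesis in 4.1, which speaks only of improvement in both arms, with the between-arm comparison in 9.1 and 9.2.

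The cost is wording. The test, alpha and decision rule stay as they are, and the first two points need no further participants. The SD point needs either the SD of change or an explicit range before the adequacy of N can be confirmed.
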